## **C.3. Trial (Aim 3)**

**Rationale:** We will demonstrate the impact of using LIITAH on decreasing calories purchased from restaurants by adolescents, along with the number of visits to restaurants and the impact on their BMI.

**Overview:** The trial will consist of 2 arms (an intervention and a control arm) over the course of 3 months.

**Intervention Group** – Will receive the full version of the LIITAH app which consists of 5 components that allow 1) Enhanced Location Identification (ELI), 2) Self-report of Nutrients by Annotated Photos (SNAP), 3) delivery of individually and culturally tailored point of purchase (POP) prompts along with tailored messages sent at other times of day (determined by the participant), 4) use of the app in connection with parents, 5) goal setting capacity, and 6) a point system.

**Control Group** – Will receive a version of the app with only the ELI and SNAP components. Thus, it will detect their presence in a restaurant and allow users to document their purchases by submitting annotated photos, but it will not deliver any POP prompts encouraging them to make healthy choices, or messages at other times of day. It will not allow goal setting or assign points. The control parents will receive a version of the app with only the ELI system to detect when they are in an eating venue and the SNAP component so they can submit and annotated photo of any food they purchase from a restaurant for their adolescent.

**Primary Outcome** – Data regarding the number of calories purchased will be calculated based on the photos submitted and the calorie content as listed in the nutrition information from the restaurant. Comparisons will be made between groups to determine the impact of the program on calories purchased. In addition, 24-hour food recalls will be conducted in the baseline week and final week (3 per week) to provide a comparison assessment of caloric intake from restaurants and to explore changes in caloric intake overall.

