While photo documentation decreases cost, compared to 24-hour food recalls, it may have an intervention effect. The possibility exists for the Hawthorne effect (i.e., recording may alter behavior) to cause a decrease in the calories purchased by the control group. However, we anticipate that this will be negligible as adolescents take pictures (e.g., Instagram, snapchat) of things like their food frequently, making it unlikely that the control group will be significantly impacted by submitting pictures of their food purchases.

**Secondary Outcome A** – The number of times the app identifies that users are in a restaurant will be recorded automatically and compared between groups to reveal the program's impact on restaurant visits.

**Secondary Outcome B** – Height and Weight will be obtained at enrollment and post-intervention sessions to determine potential changes in BMI. Though it is likely that use over a longer time will be needed to achieve a statistically significant decrease in BMI, these measures will be obtained to determine if a trend towards a decreased BMI will be demonstrated by the intervention group.

**C.3.a. Population and Recruitment.** We will recruit a total of 150 adolescent/parent dyads from schools, hospitals and places of worship using the methods described above, to participate in the trial, with the goal of recruiting approximately one third of the participants from each of the 3 ethnic groups targeted for this trial. In addition, within each ethnic group we will recruit adolescents in the normal weight, overweight and obese categories (a third each). Recruiting 150 dyads will allow for an expected attrition rate of 20% and still provide the 120 dyads needed to have the power to detect the anticipated changes. Inclusion Criteria: Adolescents 13 – 17 years of age, who eat restaurant food at least 3 times per week, and have a parent who agrees to participate. The RA will contact those who text/call indicating an interest in participation. During the call a baseline enrollment session will be scheduled. Dyads will receive a \$50 gift card at baseline as an incentive for participation and an additional \$50 for each of the two follow-up assessments. A cell phone and payment for data plans will be provided for those who need these in order to participate.

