### **C.3.c. Six-Week Intervention**

**Baseline Data:** For the first 2 weeks the app will only record presence in a restaurant and ask users to submit photos of their food. In week 3 the program features will be activated for the intervention group.

**Intervention Group:** *Point of Purchase (POP) messages will encourage healthy choices when participants are noted to be in a restaurant.* Participants will be asked to keep the app running on their phone. They will receive a ping when the app identifies that they are in a fast food restaurant followed by a POP prompt, tailored to their preferences and the options available at that location. If they are in a venue without a menu (though this is unlikely as most participants in the developmental project frequented popular franchises with published menus), general healthy suggestions will be provided (such as “consider choosing smaller portions” or “does this venue sell fruit?”). If the app does not ping when they enter a restaurant, they will be asked to register that location by tapping the ‘register location’ button on the app and entering the restaurant name. For detection errors, the appropriate stored venue criteria (location, geo-fence, time of day or dwell time) may be adjusted to improve detection. Users will also be asked to take a picture of any items they buy and to annotate it with information that would help to determine the nutrients in the food. Annotations may be audio, text, or made from a selection of descriptive buttons (e.g., to indicate small, medium or large sizes).

Tailored healthy lifestyle messages will be delivered at times selected by participants. In addition to messages prompting healthy choices at the point of sale, participants will receive tailored messages promoting healthy lifestyle choices. Participants will select the timeframe during which they would like to receive these daily messages. The messages will be tailored to their values, characteristics and preferences, and will address topics such as increased physical activity, obtaining sufficient sleep, and healthy nutrition. As described above, these messages will be based on Self Determination Theory and use motivational interviewing approaches.

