#### **C.3.d. Data Collection**

*Quantitative Data Collection* – The app will automatically collect number of visits to restaurants. It will also collect usage data such as how often participants submit pictures and whether they include annotations. In addition, as a gold standard, pre-post 24-hour food recalls will be performed to assess caloric intake. Post intervention sessions will be conducted to measure final heights and weights.

*Qualitative Data Collection* – At the completion of their 3-month participation (or earlier if drop out seems to have occurred – i.e., they do not use the app for a 3-week period), adolescents will participate in a semi-structured interview. Location data will be used to inform the questions in the interview. For example, participants who, based on the GPS, have not visited restaurants will be asked to share reasons for this change. Those who, based on the GPS, continue to visit restaurants will be asked about the choices made, and what if anything would be most helpful to them when they are making the choice regarding what to purchase. They will also be asked about the user interface, cultural tailoring, and the SNAP component.

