#### **C.3.e. Analyses**

Primary Outcome – Calories purchased (by and for adolescents) will be assessed using annotated photos, and nutrition data from restaurant menus (e.g., if the participant submits a picture of McDonald’s fries and indicates that it is a small order, then from the McDonalds menu, we will determine that the calories purchased were 240 kcals). Number of visits will be obtained from the app. We will use population averaged generalized estimating equation regressions (GEE) to compare trajectories of calories purchased and number of visits between groups. The GEE approach allows us to account for the correlation in repeated observations collected from subjects over time. For calories purchased, we will perform GEE linear regression modeling as a function of time, treatment group (intervention vs. control) and the interaction of time by treatment group ( $Y = \beta_0 + \beta_1 Time + \beta_2 Treatment + \beta_3 Time * Treatment + \epsilon$ ). Residual diagnostics will be performed to examine departures from model assumptions. If needed, we will use transformed outcome variables and refit the models.

Secondary Analyses – Similarly, for the number of visits by the adolescents to restaurants, we will fit a GEE Poisson regression model as a function of time, treatment group (intervention vs. control group) and the interaction of time by treatment group. For change in BMI, we will perform multiple linear regression of change as function of initial BMI and treatment group. We will add participant characteristics to the models discussed above and explore associations between the outcomes and covariates of interest (e.g. extent of app use, initial BMI (adolescent and parent), race/ethnicity). In additional exploratory analyses, using methods described above, changes in calories purchased from restaurants as assessed by the 24-hour recalls will also be examined to compare findings with the photo documentation method of assessing calories. Pre-post changes in total calories reported via the 24-hour food recalls will also be calculated and compared between groups.

Power – The trial will be powered on average calories purchased in restaurants. The average child consumes 765 calories per meal eaten away from the home and the average child eats 2.5 meals per week away from the home. While the trial population eat out more often at baseline, this conservative estimate was used in the

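### The exploratory recall-versus-photo comparison sets two pre-post changes side by side and is too imprecise to say much about the photo measure; matching by calendar day would use the same data better

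*Combined protocol and SAP*

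**What the plan says.** Section C.3 (Primary Outcome) schedules the recalls: "24-hour food recalls will be conducted in the baseline week and final week (3 per week) to provide a comparison assessment" of restaurant calories, and also to explore change in overall intake. Section C.3.d describes their role as follows: "as a gold standard, pre-post 24-hour food recalls will be performed to assess caloric intake". Section C.5 gives a further use, looking for compensatory eating at home.

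The analysis is in C.3.e, under secondary analyses. It opens "In additional exploratory analyses, using methods described above", and continues "changes in calories purchased from restaurants as assessed by the 24-hour recalls will also be examined to compare findings with the photo documentation method". The documents give no matching of recall days to photos, no agreement statistic, no precision and no rule for what would count as confirmation.

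Two other places bear on the point. On the baseline period, C.3.c says "For the first 2 weeks the app will only record presence in a restaurant" and collect photos; the intervention features start in week 3. The point system described under C.1 rewards submitting a meal photo and rating the meal, with extra points for a healthy rating. The control version described in C.3 has no points.

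**The concern.** Restaurant meals are sparse relative to three recall days, so a pre-post change built from those days is dominated by which days were sampled. Setting that change beside the photo change compares a very noisy estimate with the one it is meant to check.

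At stake is the ability to see whether photo capture differs between arms. From week 3, intervention adolescents have a reason to submit photos, and a particular reason to submit healthy ones, that controls lack. A capture difference arising then would enter the time-by-treatment term of the primary model. The documents do not show which direction it would take: more photos raise recorded calories, while selective submission of healthier meals lowers them.

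For scale, suppose that a meal without a photo adds nothing to the total. At 2.5 meals/week x 765 kcal = 1,912.5 kcal/week, a capture gap of 10 points between arms is worth about 191 kcal/week, and a gap of 20 points about 383 kcal/week, against a target difference of 650.

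**Working it through.** **Inputs from the documents**
- Three recall days in each of two weeks (C.3).
- Meal frequency (C.3.e): "the average child eats 2.5 meals per week away from the home". Entry floor (C.3.a): adolescents "who eat restaurant food at least 3 times per week".
- Meal size (C.3.e): "The average child consumes 765 calories per meal eaten away from the home".
- 60 per arm, difference 650 kcal/week, SD 1,200 kcal, two-sided 5% (C.3.e, Power).

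**Assumptions not in the documents:** Poisson visits, meals of constant size, recall days spread at random over the week, the share f of variance that is stable between persons, the photo capture rates, and a design effect of 1.5.

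**The plan's own figure.** SE = 1200 x sqrt(2/60) = 219. Power = Phi(650/219 - 1.96) = 84% (83.7% by exact t-test), against the stated 80%. The stated size is conservative, and 60/0.8 = 75 per arm reproduces. This concerns the photo outcome; the plan states no precision for the recall comparison.

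**Meals in three recall days**
- Expected number: 2.5 x 3/7 = 1.07; 3 x 3/7 = 1.29.
- Chance of none: exp(-1.07) = 34%; exp(-1.29) = 28%. At an assumed 5 per week, 2.14 meals are expected and 12% of adolescents have none.
- Correlation of a 3-day total with the same week's total: sqrt(3/7) = 0.65, even if every photo is perfect.

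**Power of the recall change, Poisson visits**
- SD of a 3-day total scaled to a week: 765 x sqrt(1.07) x 7/3 = 1,848; at 3 per week, 2,024.
- SE of the arm difference in change, periods independent: SD x sqrt(2) x sqrt(2/60) = 477; 523.
- Power for 650: Phi(650/477 - 1.96) = 28%; Phi(650/523 - 1.96) = 24%.

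**Allowing stable differences between persons.** Start from the plan's SD of 1,200. The within-person variance is (1 - f) x 1200² x 7/3, and the change SD is the square root of twice that.

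| f | SD of change | Power (t-test) | 95% half-width, kcal/week |
|---|---|---|---|
| 0 | 2,592 | 28% | 928 |
| 0.25 | 2,245 | 35% | 803 |
| 0.5 | 1,833 | 49% | 656 |
| 0.75 | 1,296 | 78% | 464 |

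Pure meal-count variation gives 765 x sqrt(2.5) = 1,210, close to the plan's SD of 1,200. That points to the low end of f.

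**How much is due to change scoring.** With complete 7-day records in each period, the Poisson SDs are 1,210 and 1,325, the SEs 312 and 342, and the power 55% and 48%.

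**What the same recalls give if matched by date**
- 120 completers x 1.07 to 1.29 = 129 to 154 restaurant meals per recall week.
- Half-width around an assumed 80% capture: 1.96 x sqrt(0.8 x 0.2/129) = 6.9 points; with 154 meals, 6.3. With a design effect of 1.5: 8.5 and 7.7.
- Per arm and period, 64 to 77 meals: 9.8 to 8.9 points.
- Power for a difference between arms in the final week: 70-78% for 80% v 60%, and 26-30% for 80% v 70%.

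**The case against.** The strongest reply is that the analysis is labelled exploratory, the primary test does not depend on it, and no rule lets the recalls overturn the photo result. That stands, and it limits the point to an improvement. The recalls also serve overall intake and home compensation, which sparse restaurant meals do not undermine, and C.3.d uses its strongest description of them for caloric intake, not for the photo check.

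The low power is partly a product of change scoring: even full 7-day records reach only 48-55% under the same model. If the recall change were instead adjusted for baseline, as C.3.e does for BMI, power would be 49-67% for f from 0 to 0.5 and 87% at 0.75. This softens the figure, but the result stays weak unless most of the variance is stable.

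The entry criterion is a floor, so many adolescents will eat out more often and fewer will have no meal in a recall week. Under Poisson visits this does not rescue the change comparison. At 5 per week the SD is 765 x sqrt(2.14) x 7/3 = 2,613, the SE is 675 and power is about 16%. Under a favourable alternative (exactly three meals every week, at most one a day), the SD is 765 x sqrt(0.49) x 7/3 = 1,249, the SE is 322 and power is about 52%.

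Three stronger readings are tempting, and the documents do not support them.
- **The recalls can never confirm or refute the photos.** The pooled meal counts above show that they can inform a group-level check if matched by date. The weakness lies in the planned comparison.
- **The recalls are the only independent check.** The app records restaurant visits automatically (C.3 Secondary Outcome A, C.3.d), so detected visits against photos also reveal missing photos, though not calories.
- **A baseline week contradicts the two-week baseline.** One week can lie inside the two; the text only needs to say so.

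**Conclusion.** The point holds as a cheap improvement to an exploratory analysis. As planned, the recall-photo comparison has about 24-28% power for 650 kcal/week under Poisson visits. It has 28-49% if up to half the variance is stable between persons, and 78% at three quarters. Agreement or disagreement between the two changes would therefore say little about the photo measure. These figures rest on the assumptions listed above, applied to the plan's meal frequency, meal size, SD and 60 per arm.

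The point does not show that the primary outcome is biased. It shows that capture could differ by arm, because points are given in one arm only, and that the planned check is poorly suited to detecting this.

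**What to change.** In C.3.e, make the recall-photo comparison on the same calendar days. For each recall day, link recalled restaurant meals to adolescent and parent photos for that date. Report by arm and by period, with confidence intervals that allow for several meals from one adolescent:
- the share of recalled restaurant meals that have a photo (main measure);
- the mean kcal difference between recall and photo.

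State that recalls measure intake while photos measure purchases, so some difference is expected even with perfect recording. Keep the recall-based pre-post change in restaurant calories as exploratory, and say that it will not be read as confirming or refuting the photo result.

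In C.3, state that the baseline recalls fall within the two-week record-only window of C.3.c.

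The cost is wording in two sections and a merge by date; the number of recalls is unchanged. The limit is modest precision: about 6 to 7 points either way overall per recall week and 9 to 10 per arm and period around an assumed 80% capture, wider if meals cluster within adolescents. Only large differences between arms in capture would be detected.

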**C.3.b. Enrollment Session.** Consent/assent will be obtained and height and weight will be measured for adolescents and their participating parents. They will individually complete an online enrollment survey addressing demographics, baseline characteristics, preferences, their level of interest in making dietary changes and any specific changes they wish to make. Adolescent/Parent dyads will download [the LIITAH app](#) and receive instruction in its use and ways to tailor features to their preferences (e.g., graphics, language).

Ame00105576 The focus group part of the study has been completed for both parents and all teens on 9/2020. Due to the COVID-19 situation that hampers physical contact, recruitment for the research study trial (to replace the in-person enrollment sessions due to the COVID situation) will be conducted virtually through UMHealthResearch.org and through a Facebook and Instagram advertising campaign managed by MICHR and linked to our UMHealthResearch study page.

**Randomization:** The technology team will randomly assign dyads as they enroll to either the intervention the control group. They will then adjust the functionality of the app for the participants accordingly, and will send a message to their phone indicating their group assignment, along with instructions for their group.

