power calculation. Programs for youth suggest benefits from a 250 kcal deficit per day. We determined that a clinically significant change would be a minimum decrease of 650 kcal/week. A sample size of 60 in each group (intervention vs. control group) will have 80% power to detect a difference of 650 kcal/week using a two group t-test with a two tailed alpha of 0.05 and a standard deviation of 1200 kcals. Thus by recruiting 75 adolescents per group even with a 20% attrition we will have the power to detect the expected results.

**Qualitative Analysis** –From the post-trial interviews and the satisfaction survey we will identify participants' perceptions of the intervention overall and of the messages specifically, using the qualitative methods described above. We will explore potential differences for parents' vs adolescents' and by race/ethnicity.

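### Recruitment is structured by ethnicity and weight category, but no blocking or stratification is described and the calories and visits models do not adjust for either factor

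*Combined protocol and SAP*

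**What the plan says.** - **Recruitment (C.3.a).** The target is 150 dyads, with the goal of "recruiting approximately one third of the participants from each of the 3 ethnic groups". In addition, "within each ethnic group we will recruit adolescents in the normal weight, overweight and obese categories (a third each"). This makes a grid of nine cells with about 16 or 17 dyads each.
- **Allocation (C.3.b, Randomization).** "The technology team will randomly assign dyads as they enroll to either the intervention the control group". The rest of the paragraph concerns setting the app's functions and notifying participants. No ratio, sequence generation, blocking, stratification, minimisation or concealment is described.
- **Arm sizes (C.3.e, Power).** "Thus by recruiting 75 adolescents per group" implies a 1:1 ratio, but nothing in C.3.b produces that split.
- **Models (C.3.e).** The calories GEE and the Poisson GEE for visits have time, treatment and their product. The BMI-change regression has initial BMI and treatment. Participant characteristics, with initial BMI and race/ethnicity among the examples, are then to be added to explore associations.
- **Baseline (C.3.c).** The app only records for two weeks; the intervention features start in week 3.

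**The concern.** The plan takes trouble to fill a two-factor grid and then uses neither factor in the allocation as described or in the main models for calories and visits. The Significance section gives some reason to think ethnicity matters: it reports poorer treatment outcomes in Black and Hispanic adolescents. It also reports that the team's own clinical programme gave results that did not vary by race.

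In a trial of 120 to 150 dyads, a visible imbalance in one of these factors is an easy target for criticism. If the course of restaurant calories over time differs by category, the imbalance also adds avoidable error to the time-by-treatment estimate. Both factors are known at enrolment, so the protection is cheap.

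**Working it through.** **1. The plan's own figure.** Inputs from C.3.e: difference 650 kcal/week, SD 1200, two-sided alpha 0.05, power 80%.

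n per group = 2 × (1.960 + 0.842)² × (1200/650)² = 2 × 7.849 × 3.408 = 53.5, so 54 (55 with the t distribution). The plan says 60, at which t-test power is 83.7%, so its figure is conservative. The attrition step reproduces: 60/0.8 = 75.

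**2. Arm sizes, assuming simple 1:1 randomisation of 150.** The size of one arm is Binomial(150, 0.5).
- P(exactly 75/75) = 0.065; the 95% range is 63 to 87.
- t-test power after 20% attrition in each arm: 83.7% at 75/75, 83.5% at 70/80, 83.1% at 65/85, 82.8% at 63/87.
- Power first falls below 80% at 52/98, and a split that uneven or worse has probability about 0.0002.

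**3. Category balance, same assumption.** For one category holding a third of the dyads, the SE of the between-arm difference in its share is about √[(1/3)(2/3)(2/75)] = 0.077. A 10-point gap is 0.10/0.077 = 1.30 SE, two-sided probability 0.19. Simulation with nine cells of 16 or 17 gives:

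| Gap of at least | One given category | At least one of six |
|---|---|---|
| 10 points | 0.19 | 0.62 |
| 15 points | 0.06 | 0.26 |
| 20 points | 0.01 | 0.05 |

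**4. Effect on the primary contrast.** If the change over time in one category differs from the rest by D kcal/week and the arms differ by a share s in that category, the contrast shifts by s × D. The documents give no value for D. For an assumed D of 200 to 600 and s of 0.10 to 0.20, the shift runs from 0.10 × 200 = 20 to 0.20 × 600 = 120 kcal/week, against the target of 650.

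**5. Which adjustment helps.** With complete data on a common schedule and an exchangeable working correlation, the time-by-treatment estimate in the linear GEE is the difference between arms in mean within-person slope. A main effect of ethnicity or weight category is constant over time, so it leaves slopes alone. Factor-by-time terms act on them. In an illustrative simulation with complete data, the SE of the time-by-treatment term was 154.7 without the factors, 154.7 with main effects only, and 134.6 with factor-by-time terms under an assumed difference in trajectories. That illustration is generous: 134.6/154.7 = 0.870, and 1 − 0.870² = 0.24, so it corresponds to the factors explaining about 24% of slope variance. If they explain an assumed 2% to 10%, the SE is multiplied by √0.98 = 0.990 to √0.90 = 0.949, and power at 60 per group becomes 84.4% to 87.3%, against 83.7%.

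**6. Balance under stratified blocks.** With nine strata and blocks of 4 (an assumed size), no simulated list went beyond 72/78, and 97% had arms within 4 dyads of each other. If cells fill as 17 + 17 + 16, only the two cells of 17 leave one dyad over, so a category of 50 splits no worse than 26/24. The largest gap in share is then about 26/74 − 24/76 = 0.036, or 3.6 points.

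**The case against.** Several objections stand, and they limit the point.

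- **A reader might infer that the analysis ignores both factors.** It does not. C.3.e names race/ethnicity and initial BMI for exploratory models, and the BMI-change model already adjusts for initial BMI. The gap is in the pre-specified calories and visits models.
- **A reader might infer that failing to reach 75 per arm leaves the trial underpowered.** Step 2 shows otherwise.
- **A reader might infer that the plan states simple randomisation.** It is silent. Assigning dyads as they enrol is compatible with a blocked list, and the power text implies equal arms. Every probability in steps 2 and 3 rests on that assumption.
- **Randomisation keeps the unadjusted test valid.** Chance imbalance is already covered by correct standard errors. Because there is a pre-activation baseline, a stable difference between categories drops out of the time-by-treatment contrast; only differing trajectories matter, and their size is unknown.
- **Large gaps are uncommon**, and a 20/30 split in an ethnic group of 50 raises the SE of a within-group contrast by only 2.1%: √[(1/20 + 1/30)/(2/25)] = 1.021. No within-ethnicity treatment test is planned.
- **A reader might see a conflict of interest in the technology team making the assignment, cured by moving it to the university.** The Commercial Potential section gives the university and the company the same licensing intention. Protection comes from generating and concealing the list in advance, not from which party holds it.

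A recruitment quota also does not by itself oblige a trial to stratify. Still, none of this gives a reason to leave both factors out of the allocation and the primary model when they are recorded at enrolment.

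**Conclusion.** The point holds as a design improvement worth making, not as a threat to validity or to the stated power. Under the assumption of simple 1:1 randomisation, a gap of 10 points or more in at least one of six categories is more likely than not (0.62), while a gap of 20 points or more is unlikely (0.05). The cost is some precision in the time-by-treatment contrast, of a size that depends on how far trajectories differ by category, plus the loss of credibility that follows a visible imbalance. On an assumed 2% to 10% of variance explained, adjustment is worth roughly 1 to 4 points of power. Adjustment by main effects alone would achieve almost nothing for the primary contrast.

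**What to change.** 1. In C.3.b, state a 1:1 ratio and a concealed list generated before enrolment, in permuted blocks of mixed small sizes, stratified by ethnicity (3) and weight category (3). The technology team only executes the list.
2. In C.3.e, pre-specify ethnicity and weight category, and the interaction of each with time, in the calories and visits GEE models. Main effects alone are not enough (step 5).
3. Add ethnicity to the BMI-change model, which already has initial BMI.

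Cost: a paragraph in the protocol and a list loaded into a system that already makes the assignment. Demographics, height and weight are already collected at the enrolment session. The downsides are a few extra model parameters and slight residual imbalance from incomplete blocks in nine strata.
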